Preoperative levels of depressed mood and anxiety have been linked to PPP at 1 yr after TKR. Pain anxiety and pain catastrophizing are also implicated in the development of PPP after surgery. Pain anxiety is defined as the tendency to have fear-like symptoms when pain is anticipated or experienced. A crucial component of the pain anxiety construct for the proposed study is “behavioral avoidance.” This component describes the tendency to avoid movement because of fear of pain due to movement. Patients scoring high on behavioral avoidance may tend to restrict movement of their operated knees, leading to poor range of motion and PPP. Pain catastrophizing is defined as the tendency to magnify and ruminate on the most negative aspects of pain. High pain catastrophizers tend to report higher pain intensity because they focus considerably more attention on how awful the pain may be. The mechanism by which catastrophizing is thought to impact the experience of pain is by promoting sensitization or interfering with pain inhibition in the central nervous system. In OA patients, catastrophizing has been associated with high pain intensity and hyperalgesia (to electrical stimulation). Studies have shown that preoperative pain catastrophizing was predictive of PPP after TKR.

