Surgical trauma induces neuroplastic changes in pain sensitivity, so that mechanical hyperalgesia can be demonstrated in both the area of inflammation (primary hyperalgesia) and in the non-inflamed surrounding tissue (secondary hyperalgesia). Primary hyperalgesia depends mainly on sensitization of peripheral nociceptors while secondary mechanical hyperalgesia occurs as a result of central sensitization in the spinal cord. Central sensitization is thought to be triggered by C-fibre nociceptive input, with activation of NMDA receptors in the spinal dorsal horn. Once central sensitization is established, dorsal horn nociceptive neurons become sensitized to previous sub-threshold stimuli and input from low threshold mechanically sensitive fibers (A- $\beta$ ). This process is accompanied by a spread of sensitivity well beyond the peripheral site of injury, termed secondary hyperalgesia. Recent studies have employed a technique to measure the *area of punctate mechanical hyperalgesia* surrounding thoraco-abdominal surgical wounds. We propose to use punctate mechanical testing in the area around the knee to assess the development of secondary hyperalgesia after TKR. In neuropathic pain conditions, it is hypothesized that central sensitization and secondary hyperalgesia persist over time so that a chronic pain state is established, and the same sequence of events most probably contributes to PPP after TKR. Moreover, it is important to note that the significance of studying the area of punctate mechanical hyperalgesia surrounding the surgical wound goes beyond basic understanding of a mechanism contributing to PPP. Unlike other potential neurobiological mechanisms (e.g. cytokines), the procedure for assessing secondary hyperalgesia can be swiftly implemented by personnel in clinical settings at a low cost (although some training is required). Thus, our proposal gains significance with regard to actual clinical practice and treatment decision-making insofar as this potential neurophysiological risk factor – secondary hyperalgesia – can be readily and frequently measured by the practitioners administering care to the TKR patient.

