Analgesic Consumption	X	X	X	X	X	X	X	X	X
Knee X-Ray Medical Chart Results	X						X		X
Pain Intensity	X	X	X	X	X	X	X	X	X
Neurophysiologic Assessments	X		X						X
Functional Tests	X		X	X	X	X	X	X	X
Psychosocial tests	X								X

\*ROM will be the only functional test assessed at 36, 48, and 72 hours

**Screening and recruitment feasibility:** A research coordinator/nurse (RN) will screen patients scheduled for Drs. [name] (Co-Investigator), [name], [name], [name] and [name] (participating orthopedic surgeons) to undergo TKR using the criteria detailed below. We will recruit 100 patients/yr. Patient recruitment will be completed within 36 mo; however the 6- mo follow-up extends the study period to a total of 3.5 yrs. If a patient meets study criteria, the RN will contact the patient to obtain verbal consent and assess study eligibility. Selection for inclusion will not be based on race or socioeconomic status.

**Inclusion & exclusion criteria:** *Inclusion Criteria* are: (1) undergoing standard tricompartmental primary TKR; (2) 18- 85 yrs of age; (3) knee to be replaced is the primary source of patient's pain; (4) patient agrees to preoperative and follow-up visits and to comply with the assessment tests; (5) patient consents to standard anesthetic and analgesic protocol, with medical care as deemed necessary by the anesthesiologist, and has no contraindications. (6) Patient has been diagnosed with osteoarthritis. *Exclusion criteria* will include: (1) chronic opioid use  $\geq$  10 mg/day of morphine equivalents within one wk prior to the surgery, and duration of use  $>$  4 wks; (2) history of opioid abuse; (3) inability to understand and communicate with the investigators to complete the study related questionnaires ; (4) patient is planning to undergo another elective joint replacement procedure during the 6-mo period of participation; (5) any co-morbidity which results in severe systemic disease limiting function {as defined by the American Society of Anesthesiology (ASA) physical status classification  $>$  3} (6) taking medication for severe depression .

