**(2) Neurophysiologic Assessment:** The following neurophysiologic assessments will be performed at the Department of Anesthesiology Clinical Research Section (Room 1487 Jelke), where the PI or Co-PI ([name]) will supervise the RN in the performance of these tests. These assessments have been performed by the PI and [name] (Co-investigator) for other clinical and basic research respectively.

**(a) Thermal pain stimulation:** Prior to surgery, a heat probe (3x3 cm; TSAll instrument; Medoc®) will be applied 16 cm above the center of the patella as a measure for **thermal pain sensitivity**. Probe temperature will be ramped up from 32° C at a rate of 4°C/sec until 47 °C is reached, and then maintained for 5 sec. After the 5 sec period, subjects will rate pain intensity (0-10 NRS scale). If subject requests removal of probe before 5 sec period due to intolerable discomfort, it will be removed and a maximal value of 10 will be given. The test will be repeated 4 times and the average of the responses will be calculated. This procedure will be repeated on the contralateral leg. **(b) Examination of the knee for peripheral neuropathic pain (StEP)** using the following 9 parameters and calculating a score to determine the presence of neuropathic pain (total score ≥ 4). The StEP will detail the symptoms and signs of the pain in the knee. This test will be performed 5 cm medial and 5 cm rostral to the center of the patella on the un-operated knee as a control and then the operated knee.

- Sympathetic: Recording of skin characteristics (yes/no evaluation of color, sweating, trophic changes)
- Tactile allodynia (touch): Numbness, allodynia or hyperalgesia to von Frey filament stimulation, with corresponding NRS pain intensity
- Tactile hyperalgesia (blunt pressure): Decreased or increased response, with corresponding NRS pain intensity
- Dynamic tactile allodynia (brush movement): Decreased or increased response, with corresponding NRS pain intensity
- Vibration sense (tuning fork): yes/no to decreased response to stimulation at the tibia bone ventral midline, 15 cm below lower point of proposed incision
- Evoked pain (pinprick): decreased or increased response, with corresponding NRS pain intensity
- Non-painful warm stimulus (TSAll instrument, Medoc®): decreased or increased response, with corresponding NRS pain intensity

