contacted and the epidural infusion titrated (per previous published protocol). However, if these measures fail and the patient has severe pain, intravenous opioids (morphine 2 mg bolus) will be administered. Records will be kept of the total amount of epidural solution consumed, including morphine boluses, in increments of 4h for the 24h postoperative period. After 24 hours, the epidural catheter will be removed. We customarily administer warfarin (oral 5 mg) for deep venous thrombosis prophylaxis on the night of TKR. An International Normalized Ratio will be obtained prior to removing the catheter. Once the epidural catheter is removed, all patients will receive hydrocodone 10 mg/acetaminophen 325 mg, 1-2 tablets every 4-6h depending on the NRS pain score for a maximum of 6 tablets/ day (to keep within current geriatric guidelines <3.25 mg/day acetaminophen), until discharged from the hospital. Patients having NRS  $\geq 4$  for more than 1h will receive intravenous morphine 2-4 mg as needed every 15 min for a maximum of 15 mg over a period of 2h. Patients allergic to intravenous morphine or oral hydrocodone will receive an equivalent dose of intravenous hydromorphone or oral oxycodone respectively. All analgesics administered over 0-72h will be recorded in the data collection book for inclusion as covariates in analyses. Although a more complex algorithm for pain management, including multimodal non-opioid analgesia, could be used and continued for at least 2 wks later, those analgesics might become factors themselves that influence the development of PPP, and therefore will not be used in this proposed study. We will also obtain a 5mL blood sample for RNA analysis during the hospital stay (when wound inflammation is maximum).

[figure not shown]
**Postoperative Management:** Routine vital signs will be recorded on the floor and transferred to the data collection book. The patients will undergo routine physical therapy sessions twice/daily until they meet the hospital discharge criteria as determined by the therapist.

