#### Acute Postoperative Assessments (total time approximately 30 min):

**(1) Pain Intensity:** The 11-point NRS pain intensity will be recorded every 4h for 0-72h postoperatively of the operated knee, then twice daily thereafter until discharge. The area-under-curve (AUC) for NRS over 0-72h will be calculated and interpreted as the burden of acute postoperative pain.

**(2) Neurophysiologic Assessment of mechanical (punctate) hyperalgesia and hypoalgesia** will be performed at least 6 hours after removal of epidural, post-incision by the RN under the supervision of PI. The elasticized (ACE) wrap around the knee will have already been removed at 24h post-incision. With the subject in a relaxed supine position with eyes closed, stimulation with a hand-held von Frey filament (4 g) will begin on the lateral aspect of the knee where the patient reports no pain sensation (Figure below), and move in 2 cm steps toward the incision until the subject reports a distinct change in sensation. The first point where the subject reports the sensation as 'painful', 'sore', or 'sharper', will be marked with an alcohol pen. To map the area of this mechanical sensitivity around the knee, testing will be done every 2.5 cm around the mid-line along radial lines. If no change in sensation is found, stimulation will be stopped at 5 cm from the surgical incision to restrict our testing to the area of **secondary mechanical hyperalgesia**. Any areas of numbness will also be noted. To quantify the area, a transparent plastic sheet with pre-marked grid marks will be placed over the knee to facilitate the transfer of the skin markings to our template. The area will then be measured with a digital planimetry software.

(a): In preliminary studies we found the mean area to be 37 cm^2. Areas of numbness will also be noted.

**(3) Functional Measures (ROM only):** The active and passive ROM of the knee will be recorded every day in the hospital by the physical therapist. In addition, the RN will measure active and passive ROM at least 6 hours

after removal of epidural, (performed at the same time as assessment of mechanical (punctate) hyperalgesia and hypoalgesia.

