model fit will be evaluated for all models. **Moderating** effects will be tested using model building with predefined interactions for linear or logistic models.

Due to the extensive monitoring designed into our protocol we do not expect a large amount of missing data; however, the missing data that does arise will be handled using multivariate multiple imputation. Data not assumed to be missing at random, will be evaluated for systematic effects using sub-groups stratification. Statistical analyses will be performed using SAS version 9.1 (SAS Institute Inc, Cary, NC) or SPSS (SPSS for Windows, Rel. 16.0.1. 2007. Chicago: SPSS Inc.), with statistical significance determined with a Type I error threshold of  $\alpha = 0.05$ . For continuous outcome mediation analysis we will use a SAS macro (INDIRECT macro) and for dichotomous outcomes the SPSS macro version (INDIRECT macro) will be used, as the SAS macro version does not allow for dichotomous outcome variables.

**Primary endpoint:** The *primary endpoint* for the **Primary Aim** will be the incidence of PPP after TKR (similar to our power analysis), evaluated at 6 mo. For the **Secondary Aims**, the *primary endpoint* will be functional outcomes (ROM, WOMAC, SF-36,).

**Secondary endpoints:** The *secondary endpoint* for the Primary and Secondary Aims will examine additional parameterizations of PPP at 6 mo (NRS pain non-dichotomous, StEP neuropathic pain examination). Use of raw NRS pain scores may highlight functional (e.g. linear) relationships between pain and the predictive factors. Analysis will be performed as described for the primary outcome variable (incidence of PPP) but with the re-parameterized outcome variable and different model assumptions, depending on distributional properties. Each re-parameterization will be evaluated with respect to and compared with the primary outcome.

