### **Detailed Analyses:**

**Primary Aims:** are to investigate the relationships of *risk factors* and the development of PPP at 6 mo post-TKR, through independently predictive (for clinical prediction models, Hypothesis 1) and mediated models (to reveal underlying mechanisms, Hypothesis 2). These risk factors are preop thermal pain sensitivity; anxiety and catastrophizing; postop area of secondary mechanical hyperalgesia and pain intensity.

A. **Independent Risk Factors:** Risk factors will be individually predictive of the PPP (primary endpoint):

*Hypothesis 1 is that greater (↑) preop pain sensitivity, higher levels of preop pain anxiety and catastrophizing, larger areas of secondary hyperalgesia post-TKR and higher postop pain intensity will independently predict increased incidence of PPP at 6 months post-TKR.*

- 1) **Pain Intensity:** Expected Result: (Hypothesis 1): Higher postop pain intensity (↑), will independently predict increased incidence of PPP at 6 mo post-TKR (ex. ↑ postop NRS → ↑ PPP incidence).
- 2) **Neurophysiologic:** Expected Result: (Hypothesis 1): Greater preop pain sensitivity (↑) and larger areas of secondary hyperalgesia ( $\text{cm}^2$ ) post-TKR will independently predict increased incidence of PPP at 6 mo post-TKR (ex. ↑ preop thermal pain sensitivity → ↑ PPP incidence).
- 3) **Psychosocial:** Expected result: (Hypothesis 1): is that greater (↑) catastrophizing (PCS score) will independently predict increased incidence of PPP at 6 months post-TKR (ex. ↑ PCS score → ↑ PPP).
- 4) **Demographics:** Expected result: Patients 65-85 yrs will have a lower incidence of PPP than patients 18-64 yrs.

B. **Mediation Models:** Effects of preoperative factors on development of PPP occur through interrelated neurophysiologic mechanisms:

*Hypothesis 2 is that the effects of preoperative factors on development of PPP occur through interrelated neurophysiologic mechanisms. Thus, it is expected that the area of secondary hyperalgesia post-TKR will mediate links between preoperative pain sensitivity and PPP incidence, as well as mediate links between pain anxiety/catastrophizing and PPP incidence at 6 mo after TKR.*

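### The mediator in Hypothesis 2 is mapped only after surgery, so pre-existing sensitization is a rival explanation; preoperative StEP data could reduce it in part but have no specified use

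*Combined protocol and SAP*

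**What the plan says.** **The mediator.** Detailed Analyses, B (Mediation Models), states that "it is expected that the area of secondary hyperalgesia post-TKR will mediate links between preoperative pain sensitivity and PPP incidence", and makes the same claim for pain anxiety and catastrophizing. The Significance section gives the interpretation: "We propose to use punctate mechanical testing in the area around the knee to assess the development of secondary hyperalgesia after TKR". Its Multi-Factorial Approach paragraph attributes the mechanism to heightened central sensitization after the operation in high catastrophizers, and draws a drug-treatment implication from it.

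**When it is measured.** Punctate mapping is described only under Acute Postoperative Assessments, where it "will be performed at least 6 hours after removal of epidural, post-incision by the RN under the supervision of PI". For epidural patients, "After 24 hours, the epidural catheter will be removed", so mapping falls at about 24 + 6 = 30 h or later. The Study Calendar row "Neurophysiologic Assessments" is marked at Preop, 36h and 6 mo. In the text, however, the preoperative tests are thermal stimulation and StEP, and the 6-month test is StEP alone. No area is mapped before surgery or at 6 months.

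**What is collected before surgery.** StEP is done at one point on the un-operated knee and then on the operated knee. It includes "Numbness, allodynia or hyperalgesia to von Frey filament stimulation, with corresponding NRS pain intensity", blunt pressure, pinprick and temporal summation.

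**What is used.** The Covariates paragraph lists age, weight/BMI, OA severity and ASA status as preoperative terms. StEP is named for analysis only in Secondary endpoints, among "additional parameterizations of PPP at 6 mo (NRS pain non-dichotomous, StEP neuropathic pain examination"). No baseline StEP term is given there, in the hypotheses or in the example prediction equation.

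**The concern.** A mediation claim needs the mediator to carry the effect of the exposure, not merely to share a cause with exposure and outcome. Everyone enrolled has osteoarthritis and a painful knee. The plan itself notes hyperalgesia in such patients before any operation: "In OA patients, catastrophizing has been associated with high pain intensity" and, in the same sentence, with hyperalgesia to electrical stimulation. Catastrophizing is one of the Hypothesis 2 exposures.

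Suppose a patient arrives already sensitized. The preoperative thermal rating is higher, the postoperative area may be larger because it was partly there beforehand, and PPP may be likelier for the same reason. The planned models would then show an exposure-to-area path and an area-to-PPP path even if surgery-induced hyperalgesia did nothing.

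At stake is the mechanistic reading of a primary aim, and the inference that treating postoperative hyperalgesia in high catastrophizers would prevent PPP. A smaller matter is the 6-month StEP endpoint: without a baseline term, signs already present before surgery count toward the outcome.

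**Working it through.** The plan gives no figure for the mediation analysis. Its sample size (259 analysed, 300 enrolled) concerns acute pain as a predictor. It also gives no SD for the area, no preoperative area and no correlation among these measures. The check is therefore an illustration under stated assumptions.

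**Inputs from the documents.** n = 259, or 300 × 0.85 = 255 after the stated dropout. PPP is 46/259 = 17.8%.

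**Assumed.** Baseline sensitization B is standard normal. Thermal score T and area M each correlate r with B and are otherwise independent. The log odds of PPP depend on B only, with slope γ per SD. The true effect of M on PPP is zero.

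**Expected size of the spurious indirect effect.**
- Path a (M on T): slope = r².
- Path b (PPP on M given T): about γ × r/(1 + r²), from the regression of B on T and M.
- Product: about γr³/(1 + r²).

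The table has γ = 0.6 and n = 259, with 2,000 runs per setting (400 at r = 0.7):

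| r | Formula | Simulated | Both paths P < 0.05 | Sobel P < 0.05 |
|---|---|---|---|---|
| 0.3 | 0.6 × 0.027/1.09 = 0.015 | 0.014 | about 4% | under 1% |
| 0.5 | 0.6 × 0.125/1.25 = 0.060 | 0.058 | about 26% | about 17% |
| 0.7 | 0.6 × 0.343/1.49 = 0.138 | 0.136 | about 32% | about 30% |

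With r = 0 the joint rate is 0 to 0.2%. Adjusting for true B brings the indirect effect to about 0 and the joint rate to 1% or less. The baseline is therefore what drives the false positives.

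**What a StEP-like proxy achieves.** Let the proxy correlate ρ with B, so that its reliability is ρ². Take r = 0.5 and γ = 0.6.
- Path a becomes r²(1 − ρ²)/(1 − r²ρ²).
- Path b becomes γ × [r/(1 − r²)] / [1 + 2r²/(1 − r²) + ρ²/(1 − ρ²)].
- ρ = 0.5: a = 0.1875/0.9375 = 0.200; b = 0.6 × 0.667/2.000 = 0.200; product 0.040 (simulated 0.037). Joint rate about 18%.
- ρ = 0.7: a = 0.1275/0.8775 = 0.145; b = 0.6 × 0.667/2.628 = 0.152; product 0.022 (simulated 0.022). Joint rate about 9%.

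**Wider range.** n = 255, r from 0.3 to 0.6, γ from 0.3 to 0.7 (odds ratio e^0.3 = 1.35 to e^0.7 = 2.01 per SD), intercept −1.7:
- No baseline term: about 2% to 40% by joint significance; below 1% to 35% by Sobel.
- Proxy of reliability 0.25 (ρ = 0.5): about 1% up to 27% to 31% by joint significance. The top figure differs between repeat runs.
- Proxy of reliability 0.6 (ρ = √0.6 = 0.77): about 0.3% to 14%.
- At r = 0.2 the unadjusted joint rate is below 2%.

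The low end arises at r = 0.3, the high end at r = 0.6 with γ = 0.7. Bootstrap intervals, which the plan also names, were not simulated.

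**The case against.** Several points on the other side stand.

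- **StEP is not a baseline map.** A reader might infer that the preoperative StEP scores could separate pre-existing from surgical sensitization. The documents do not support that. StEP is a mixed yes/no and NRS examination at one point on an arthritic knee. The Significance section distinguishes primary (peripheral) from secondary (central) hyperalgesia, and mapping stops 5 cm from the incision to stay in the secondary zone. An operated-knee StEP score may largely reflect the primary kind. Nothing in the documents gives its reliability as a proxy.
- **The size is assumed.** At correlation 0.3 the false-mediation rate is only a few percent, and under Sobel it is below or near 1%. OA severity, a planned covariate, was not in the simulation and may absorb some of the bias.
- **Pre-existing sensitivity is partly modelled.** In the first Hypothesis 2 model the thermal score is the exposure, so the area-to-PPP path is conditional on it. The simulation already conditions on it, and the error persists at moderate correlations.
- **Over-adjustment.** The Significance section has catastrophizing acting by promoting sensitization. If so, preoperative sensitization lies on the path under test, and adjusting for it removes part of a real effect. This argues against a compulsory covariate in every model.
- **Permission exists.** The pre-surgery section lets measures serve in several roles, and the omnibus models could take in StEP. Neither commits a Hypothesis 2 model to it.
- **The StEP endpoint.** Neuropathic status at 6 months is a legitimate target in itself. Adjustment serves the question of change since surgery.

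**Conclusion.** The point holds as a limit on the causal reading of Hypothesis 2. The mediator has no preoperative value, the background reads it as arising after surgery, and available preoperative mechanical data have no assigned use. If baseline sensitization correlates about 0.5 or more with both thermal score and area and also predicts PPP, a substantial share of trials with no true mediation would report it; at 0.3, few would. The documents cannot say which applies, and the ranges above rest wholly on the assumed correlations and odds ratios.

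A reader might go further and infer that the area merely marks sensitization brought into surgery. Nothing in the documents shows that; it is a rival explanation the planned models cannot exclude. Nor does it undermine Hypothesis 1, where the origin of the area matters little to prediction.

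**What to change.** In Secondary endpoints, Covariates and Detailed Analyses:

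1. Adjust the 6-month StEP analysis for the preoperative StEP score.
2. For each Hypothesis 2 model, prespecify a companion analysis that adds a preoperative StEP mechanical score (von Frey, blunt pressure, pinprick, temporal summation) to both the area equation and the PPP equation. Report it beside the model without that score. Report the un-operated knee as well, as a marker of more general sensitization.
3. Claim surgery-induced mediation only if the indirect effect persists in the adjusted analysis. State that a single-site StEP score is an imperfect baseline and that residual confounding remains.

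The cost is analysis-plan wording and one more covariate; no visit or test is added. The downside is possible over-adjustment in the catastrophizing model, which is why both versions should be shown. A preoperative area map would be the more direct baseline, but would be a new measurement.
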